7.3 Classification of an Adverse Event

7.3.1 Severity of Event

The severity of each AE will be graded on a 3-point scale and reported in detail as indicated on the eCRF:

- **Mild:** awareness of sign or symptom but easily tolerated, causing minimal discomfort, and not interfering with normal everyday activities
- **Moderate:** sufficiently discomforting to interfere with normal everyday activities
- **Severe:** incapacitating and/or preventing normal everyday activities

7.3.2 Relationship to Study Drug

The causality of each AE should be assessed and classified by the Investigator as "related" or "not related." An event is considered related if there is a reasonable possibility that the event may have been caused by the product under investigation (i.e., there are facts, evidence, or arguments to suggest possible causation).

Consider the following when assessing causality:

- Temporal associations between the agent and the event
- Response to cessation (de- challenge) or re-challenge
- Compatibility with known class effect
- Known effects of concomitant medications
- Pre-existing risk factors
- A plausible mechanism
- Concurrent illnesses

7.3.2.1 Duration

The start and stop dates for AEs will be recorded using the following criteria:

- **Start:** Date of the first episode of the AE or date of significant sustained worsening in severity
- **Stop:** Date when AE either ceased permanently or changed in severity

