Sleep Disorders Inventory ^f	X				X		X		X		
Assessment of concomitant medications/procedures	X	X	X	X	X	X	X	X	X	X	X
Assessment of AEs ^g	X	X	X	X	X	X	X	X	X	X	X
Dispense study drug ^h	X ^{i,j}	X	X	X	X	X	X	X		X	
Study drug accountability	X ^j	X	X	X	X	X	X	X	X	X	

Table footnotes and abbreviations on next page

Abbreviations: AE(s)=adverse event(s); CGI-S=Clinical Global Impression-Severity; C-SSRS=Columbia-Suicide Severity Rating Scale; ECG=electrocardiogram; EOT/ET=end-of-treatment/early termination; EQ-5D-5L=5-level EuroQol-5D; ESRS-A=Extrapyramidal Symptom Rating Scale - Abbreviated; GCAS=Global Clinician Assessment of Suicidality; MMSE=Mini-Mental State Examination

- ^a Study visits are designated by weeks and have a ± 3 -day window (Visits 2 through 5), or a ± 7 -day window (Visits 6 through 9), or a +4-day window (Visit 10) calculated from the Baseline Visit.
- ^b Subject and study partner/caregiver consent for the present study **must be** obtained for entry into the present study prior to the final procedures being performed at the end of treatment (EOT) visit in the antecedent study or early termination (ET) visit (if the study was ended early by the Sponsor). Data from the EOT/ET visit procedures of the antecedent study will be carried over as baseline information in the present study, as applicable.
- ^c A single 12-lead ECG can be performed any time before blood sampling or at least 30 minutes after blood sampling during clinic visits.
- ^d A urine pregnancy test may be performed for female study subjects of childbearing potential. If urine cannot be obtained in women of childbearing potential, a serum pregnancy test should be done in its place.
- ^e The scale used in the antecedent study should also be used in the ACP-103-047 study. If the subject was previously assessed with the C-SSRS and is no longer able to reliably complete the C-SSRS in the Investigator's judgment, the GCAS should be administered and used thereafter in the present study.
- ^f Appropriate consent/assent needs to be collected before assessment at Baseline.
- ^g All ongoing AEs from the antecedent study will be carried over after informed consent has been obtained for the ACP-103-047 study and recorded from Baseline for the present study until resolution or the follow-up safety assessment. AEs occurring after the first dose of open-label study drug until 30 days after the last dose of open-label study drug will be recorded as an AE in the ACP-103-047 study.

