6.4 Safety Follow-up

A 30-day safety follow-up telephone call with the subject and study partner/caregiver is to be completed for subjects who complete the study as well as those who discontinue prematurely from the study. Subjects should have the following completed 30 (+4) days after last dose of study drug:

- Assessment of concomitant medications/treatments
- Assessment of AEs

6.5 **Unscheduled Visits**

Unscheduled visits may occur as determined by the Investigator. The following assessments generally should be recorded at each unscheduled visit: assessment of AEs, assessment of concomitant medications/treatments, measurement of vital signs, CGI-S, ESRS-A, C-SSRS (Since Last Visit version) or the GCAS if the C-SSRS cannot be completed. The Investigator may perform any additional safety evaluations deemed to be clinically indicated.

7 **ADVERSE EVENTS**

7.1 **Adverse Events**

Adverse events occurring after the first dose of open-label study drug in ACP-103-047 until safety follow-up assessment (conducted by telephone call) 30 days after the last dose of study drug, will be recorded as an AE in the ACP-103-047 study.

All ongoing AEs from the antecedent study (ACP-103-046) will be carried over and recorded from Baseline for the ACP-103-047 study until resolution or the follow-up safety assessment. All AEs must be either resolved or stable at end of study. If ongoing at the end of the study, the subject should be referred for appropriate treatment.

7.2 **Specification of Safety Parameters**

7.2.1 **Definition of Adverse Event**

An AE is defined as “any untoward medical occurrence associated with the use of a drug in humans, whether or not considered drug related” ([US FDA 2012](#)).

An AE can therefore be any unfavorable and unintended sign (e.g., an abnormal laboratory finding), symptom, or disease temporally associated with the use of a drug, without any judgment about causality or seriousness. An AE can arise from any use of the drug (e.g., off-label use, use in combination with another drug) and from any route of administration, formulation, or dose, including an overdose.

A suspected adverse reaction is any AE for which there is a reasonable possibility that the drug caused the AE.

AEs do not include the following:

- Stable or intermittent chronic conditions (such as myopia requiring eyeglasses) that are present prior to Baseline of the ACP-103-047 study and do not worsen during the study

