7.3.2.2 Frequency

The frequency of the AE should be indicated according to the following definitions:

- **Single:** Experienced once, without recurrence
- **Recurrent:** More than one discrete episode with the same severity

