14.1 Adverse Events

All AEs, classified by preferred term, will be coded using MedDRA version 23.0 or newer.

An AE (classified by PT) will be considered a TEAE if it started on or after the OL first dose of study drug and no later than the OL last dose date + 30. AEs reported on Day 1 based on pre-dose findings will not be considered as TEAEs.

For the following summaries, the event counts and the number and percentage of subjects reporting TEAEs will be tabulated by cohort and overall:

- TEAEs by SOC and PT
- Most frequently reported TEAEs by SOC and PT
 - PTs reported by $\geq 5\%$ and $\geq 2\%$ (overall) of subjects in the Safety Analysis Set
- TEAEs by PT
- TEAEs by SOC, PT, and maximum severity
 - if more than 1 AE occurs with the same PT for the same subject, the subject will be counted only once for that PT using the most severe occurrence
- TEAEs related to study drug by SOC and PT
- Treatment-emergent serious adverse events (TESAEs) by SOC and PT
- TEAEs leading to discontinuation of study drug by SOC and PT
- AEs with fatal outcome by SOC and PT
- TEAEs with fatal outcome (that occurred within 30 days of last dose) by SOC and PT

For tabulations that include SOC and PT the display will be sorted alphabetically by SOC and then by descending subject frequency for the PTs based on counts in the Safety Analysis Set within each SOC. SOCs will not be included in the TEAEs by PT tabulation. This display will be sorted by descending subject frequency based on counts in the Safety Analysis Set.

An AE listing by subject will display all events, including those which are not TE, and will include the verbatim term in addition to the MedDRA SOC and PT. This listing will also include all relevant eCRF data associated with the event: e.g. date of onset, dose level at date of onset, date resolved, date of the first and last dose of study drug, severity, frequency, outcome, relationship to study drug, action taken with study drug, and required therapy. When a date is presented, the study day associated with the date will also be displayed. Separate listings will be presented for subjects with SAEs, subjects with AEs leading to discontinuation and subjects who died (if any). In these listings, an indicator for TEAEs will also be included.

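### AE start and stop rules do not match: an AE that eases without resolving is shown as ended or, if a site opens a second record, can be counted as a new TEAE

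*Protocol*

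**What the plan says.** **Recording.** Protocol 7.3.2.1 defines the start of an AE as "Date of the first episode of the AE or date of significant sustained worsening in severity" and the stop as "Date when AE either ceased permanently or changed in severity". Protocol 7.3.2.2 defines a recurrent AE as "More than one discrete episode with the same severity", which suggests that a record is meant to hold one severity grade.

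**Carry-over.** Protocol 7.1 says that AEs ongoing from the antecedent study "will be carried over and recorded from Baseline for the ACP-103-047 study until resolution or the follow-up safety assessment". Table S-1 footnote g agrees: they are "recorded from Baseline for the present study until resolution or the follow-up safety assessment". Neither place makes a change in severity an end point.

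**Analysis.** TEAEs are the primary endpoint (Protocol 2.1.1, SAP 2.1.1). Under SAP 14.1 an AE "will be considered a TEAE if it started on or after the OL first dose of study drug" and no later than 30 days after the last open-label (OL) dose. The one stated exception is a Day 1 event based on pre-dose findings. For the listed summaries, "the event counts and the number and percentage of subjects reporting TEAEs will be tabulated by cohort and overall". For repeat occurrences of one preferred term (PT) in the maximum-severity table, "the subject will be counted only once for that PT using the most severe occurrence". SAP 14.1 has no matching rule for event counts, and none that links consecutive records of one AE.

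**The concern.** The stop rule fires on improvement and on worsening; the start rule fires only on worsening. An AE that eases but persists is closed by one rule and not reopened by the other. The site then has two options.

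- **Open nothing.** The AE carries a stop date while it continues. Its duration is cut short and its later course is not recorded. For a carried-over AE this breaks the instruction to record until resolution.
- **Open a second record.** The start rule does not provide for this. However, the until-resolution instruction, the duty in Protocol 7.5.1 to record every observed AE, and the severity-specific frequency field could all prompt it. The new record starts during OL treatment, so SAP 14.1 classes it as a TEAE.

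Under the second option, an AE that began in the antecedent study and is getting better enters the pimavanserin TEAE table. In Cohort 1 (SAP 5.2: double-blind placebo, then OL pimavanserin) that AE may have begun on placebo. The study has no concurrent control, so nothing in the table would reveal the misclassification.

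Separately, event counts depend on how many records one AE generates.

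**Working it through.** The plan states no AE rate or event count, so there is no figure to reproduce. The check applies the written rules to example AE histories.

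**Inputs**

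- Start and stop rules: Protocol 7.3.2.1.
- TEAE test: SAP 14.1, that is, 1 ≤ start day ≤ last dose day + 30, with the first OL dose on Day 1. With a last dose on Day 364 (an example), the window closes on Day 394.
- Histories and days: invented for illustration.

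**Formula.** Records per AE = 1 + number of severity changes that open a record. That number is none if there is one record per AE, worsenings only under the literal start rule, and every change if sites also split on improvement. TEAE records are those whose start day falls in the window.

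| AE course | One record per AE | Literal 7.3.2.1 | New record at every change | TEAE events after the fix below |
|---|---|---|---|---|
| Carried over (onset Day −10), eases Day 20 | 0 | 0 | 1 | 0 |
| Carried over, eases Days 20 and 50 | 0 | 0 | 2 | 0 |
| Carried over, worsens Day 20 | 0 | 1 | 1 | 1 |
| Carried over, worsens Day 20, eases Day 40 | 0 | 1 | 2 | 1 |
| New Day 15, eases Day 30 | 1 | 1 | 2 | 1 |
| New Day 15, worsens Day 30 | 1 | 2 | 2 | 1 |
| New Day 15, worsens Day 30, eases Day 45 | 1 | 2 | 3 | 1 |

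**Reading the table**

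1. *Improving carried-over AE.* Literal reading: 0 TEAE records, but the AE has a stop date on Day 20 and no record after it. The site could enter the outcome as not resolved (Protocol 7.3.2.5), but the later course would still be lost. The false TEAE appears only in the column where sites split on improvement.
2. *Worsening OL AE.* The literal rules give 1 + 1 = 2 records, so one AE counts twice. A mild-moderate-mild course is 1 + 1 = 2 records literally and 1 + 2 = 3 if improvement also opens a record.
3. *Subject percentages.* An AE that starts in OL gives at least one TEAE record under every convention, and a subject either reports the PT or does not. The percentage is unchanged. It can change only when a carried-over AE is relabelled as a TEAE in a subject with no other TEAE of that PT.
4. *Worsening carried-over AE.* It becomes a TEAE. That is not an error.

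**Scale, by assumption.** Extra TEAE records = N × q, where q is the share of subjects with one improving carried-over AE that is given a second record. It is the product of three unknowns: the share with an ongoing AE at rollover, the share of those that ease before resolving, and the share of those for which a site opens a record. On the planned N of about 750:

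- q = 0: 0
- q = 1%: 7.5
- q = 2%: 15
- q = 5%: 37.5
- q = 10%: 75

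The documents support no value of q. Under the literal start rule the third factor is 0, and so is the product.

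**The case against.** A reader might infer that the plan turns improving AEs into TEAEs and so inflates the primary endpoint. The documents do not support that. The false TEAE needs a site to open a record that the start rule does not allow, and on the literal text none arises. Nor does mild-moderate-mild necessarily give three records; the literal count is two. Any estimate of affected subjects would rest on invented rates and on an assumption about site practice whose lower bound is zero.

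It can also be argued that Protocol 7.1 and footnote g are the specific rule for carried-over AEs. On that reading one record stays open with its antecedent start date and fails the TEAE date test. This is a fair way to reconcile the text, but Protocol 7.3.2.1 makes no exception for carried-over AEs and no passage says which rule prevails. It also leaves AEs that begin in OL and then ease without any instruction.

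Opening a new record on worsening may be a deliberate convention. That is reasonable, but the SAP does not then say whether an event in its event counts is a record or an AE.

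The eCRF, the programming conventions and the dataset specification were not available. One of them might hold a linking rule. The SAP refers to the last two for date imputation, laboratory coding and multiple measurements in a visit window, but not for linking AE records.

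The study is descriptive and tests no hypothesis, so no error rate is at risk. The TEAE table is nevertheless its main product.

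**Conclusion.** The point holds as a conflict between stated rules and a gap in counting, not as shown inflation of the primary endpoint.

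- **Certain from the text:** the start and stop rules are not complementary; a literal reading shows a continuing AE as ended; for carried-over AEs this contradicts Protocol 7.1 and footnote g; and an OL AE that worsens once counts as two events.
- **Conditional on site practice:** an improving carried-over AE counted as a TEAE. The number cannot be estimated from the documents and is 0 if no site opens a record on improvement.
- **Not affected:** subject percentages for AEs that start in OL.

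This assumes that no unseen document already links records. The change is worth making because it concerns how the primary endpoint is recorded and costs little.

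**What to change.** 1. **Protocol 7.3.2.1, or the eCRF completion guideline.** Define the stop as the date on which the AE ceased permanently, or worsened in severity, in which case a new record opens on that date. State that improvement does not close a record.
2. **SAP 14.1, TEAE test, applied first and record by record.** A record that starts on or after the first OL dose is not a TEAE if it continues a pre-dose AE of the same PT at the same or lower severity. A true worsening remains a TEAE.
3. **SAP 14.1, event counts only, applied second.** Link contiguous TEAE records of the same PT in the same subject (the next record starts on the stop date or the day after) and count them once. Keep the first treatment-emergent start date and the maximum severity.

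The order matters. If records were linked first and the chain took its earliest start date, a carried-over AE that truly worsened on OL drug could lose its TEAE status.

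**Cost.** One sentence on recording and two derivation rules. Protocol 10.7 requires protocol changes to be submitted to the IRB/EC. Steps 2 and 3 use onset date, resolution date and severity, which SAP 14.1 already lists.

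**Downsides.** True back-to-back episodes of one PT may be merged. Records made before the change, including those behind the two interim analyses in SAP 16.1, follow the old convention. Where a site closed an easing AE and opened nothing, the true stop date cannot be recovered by programming.

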7.3.2.2 Frequency

The frequency of the AE should be indicated according to the following definitions:

- **Single:** Experienced once, without recurrence
- **Recurrent:** More than one discrete episode with the same severity

7.3.2.3 Action Taken with Study Drug

- **Dose reduced:** Dose of study drug reduced
- **Dose not changed:** No change in study drug
- **Drug interrupted:** Study drug temporarily stopped
- **Drug withdrawn:** Study drug discontinued permanently

7.3.2.4 Therapy

- **None:** No new treatment instituted
- **Medication:** New treatment initiated as a direct result of AE
- **Other:** Other action required

7.3.2.5 Outcome

- **Recovered/resolved:** Recovered or resolved
- **Recovered/resolved with sequelae:** Recovered or resolved with sequelae

- **Not recovered/not resolved:** Not recovered or not resolved
- **Fatal:** Death related to AE
- **Unknown:** Unknown

7.3.2.6 Seriousness

- Not serious
- Serious

7.3.3 Definition of Unexpectedness

An AE, the nature or severity of which is not consistent with the information provided in the Reference Safety Information section of the current pimavanserin Investigator's brochure.

7.4 Time Period and Frequency for Event Assessment and Follow-up

In the event that a subject is withdrawn from the study because of an AE, the subject should be followed and treated by the Investigator until the AE has resolved, stabilized, or a new chronic baseline has been established.

7.5 Reporting Procedures

7.5.1 Adverse Event Reporting

The Investigator must record all observed AEs and all reported AEs. At each visit, the Investigator should ask the subject a nonspecific question (e.g., "Have you noticed anything different since your last visit?") to assess whether any AEs have been experienced since the last report or visit.

Note that any use of medication (and specifically any newly prescribed medication) during the course of a study may indicate the occurrence of an AE that may need to be recorded on both the AE and the concomitant medication page.

All AEs, serious and not serious, will be recorded on the AE eCRF page using appropriate medical terminology. Severity and relationship to study drug will be assessed by the Investigator.

When possible, clinical AEs should be described by diagnosis and not by symptoms (e.g., "cold" or "seasonal allergies" instead of "runny nose").

All AEs, *whether or not related to the study drug*, must be fully and completely documented on the AE eCRF and in the subject's notes.

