2.1.1 Primary Endpoints

The primary safety measure for this study is treatment emergent adverse events (TEAEs).

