4.2 Inclusion Criteria

1. Subject satisfied all entry criteria for the antecedent pimavanserin study
2. The subject may benefit from longer term therapy with open-label pimavanserin treatment in the judgment of the Investigator
3. Subject completed the antecedent study; or was participating in a pimavanserin study that the Sponsor ended early

4. Has a designated study partner/caregiver who meets the following requirements:
 - a. In the Investigator's opinion, is in contact with the subject frequently enough to accurately report on the subject's symptoms and whether or not the subject is taking the study drug
 - b. In the Investigator's opinion, is considered reliable in providing support to the subject to help ensure compliance with study treatment, study visits, and protocol procedures
 - c. Is fluent in the local language in which study assessments will be administered
 - d. Agrees to participate in study assessments, has the capacity to provide informed consent, and provides written consent to participate in the study
5. Subject can come to the clinic for study visits with a study partner/caregiver
6. Subject is willing and able to provide informed consent. Consent for the present study **must be** obtained prior to the final procedures being performed at antecedent study's EOT visit or ET visit (if the study was ended early by the Sponsor). If the subject is deemed not competent to provide informed consent, the following requirements must be met:
 - a. The subject's legally acceptable representative (LAR) (or study partner/caregiver, if local regulations allow) must provide written informed consent
 - b. The subject must provide written (if capable) informed assent
7. If the subject is female, she must not be pregnant or breastfeeding. She must also be of non-childbearing potential (defined as either surgically sterilized or at least 1 year postmenopausal) or must agree to use a clinically acceptable method of contraception or be abstinent during the study and 1 month following completion of the study.

Abstinence as a method of contraception is defined as refraining from heterosexual intercourse during the entire period of risk associated with the study treatments. This option is usually made for a specific moral, religious, legal, or health reason. If heterosexual intercourse does occur, an acceptable method of birth control is required.

Acceptable methods of birth control include the following:

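### The clinic-visit adverse-event question goes to the subject alone, so events only the study partner knows of are not sought and TEAEs in cognitively impaired subjects may be undercounted

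*Protocol*

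**What the plan says.** Protocol 2.1.1 and SAP 2.1.1 make TEAEs the only primary endpoint. Protocol 7.5.1 sets out how adverse events are found at visits. Its general rule is "The Investigator must record all observed AEs and all reported AEs". Its one scripted prompt is that at each visit "the Investigator should ask the subject a nonspecific question". It adds that use of medication, particularly if newly prescribed, "may indicate the occurrence of an AE that may need to be recorded on both the AE and the concomitant medication page".

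The partner is not mentioned in 7.5.1. Elsewhere the protocol relies on the partner as an informant. Inclusion criterion 4a (Section 4.2) asks for someone who, in the Investigator's opinion, "is in contact with the subject frequently enough to accurately report on" the subject's symptoms. Criterion 5 reads "Subject can come to the clinic for study visits with a study partner/caregiver". Section 6.4 states: "A 30-day safety follow-up telephone call with the subject and study partner/caregiver is to be completed", and that call includes an assessment of adverse events.

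**The concern.** The protocol accepts that some subjects are poor sources of information about themselves. Section 4.2 provides for consent by a representative. Sections 6.3.5.1 and 6.3.5.2 replace the C-SSRS with the GCAS when the subject cannot reliably complete it, and the GCAS includes a partner rating. SAP 8.2 has a baseline MMSE category of 10 or below. For these subjects, the prompt that feeds the primary endpoint relies on self-report if it is followed as written.

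A duty to record what is reported does not amount to asking. A partner who is not asked may not mention a fall without injury, a bout of dizziness or a few nights of confusion that has since cleared. Some sites among the approximately 100 planned will ask the partner anyway and others will not, so ascertainment may also differ by site.

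**Working it through.** The plan contains no figure to reproduce. The sample size of about 750 is not power-based and no hypothesis test is planned (Protocol 9.2 and 9.3). The check is a reading of the text, followed by an illustration of scale.

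**Step 1. Who supplies the information?**

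| Provision | Place | Informant named |
|---|---|---|
| Adverse-event question at clinic visits | Protocol 7.5.1 | Subject |
| Adverse events at the 30-day call | Protocol 6.4 | Subject and partner |
| GCAS | Protocol 6.3.5.2 | Subject, partner, clinician |
| EQ-5D-5L Proxy, SDI | Protocol 6.2.2, 6.2.3 | Partner |
| C-SSRS, MMSE | Protocol 6.3.5.1, 6.3.6 | Subject; no partner named |

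Neither document tells the site to question the partner about adverse events at a clinic visit. For the same endpoint, the closing telephone call is therefore broader than the visits before it.

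**Step 2. How long is the recall period?** Post-Baseline visits are at Weeks 2, 4, 8, 12, 16, 28, 40 and 52 (Table S-1). The intervals are 2, 2, 4, 4, 4, 12, 12 and 12 weeks. The 12-week intervals cover 52 - 16 = 36 of the 52 weeks.

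**Step 3. What do the other routes catch?**
- Vital signs, ECG, MMSE and ESRS-A at every scheduled visit show what is present on the day.
- Laboratory tests are done only at Baseline, Week 12 and Week 52, and physical examinations only at Baseline, Week 28 and Week 52.
- The medication prompt finds events that were treated.
- The recording rule captures whatever a partner volunteers.

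What remains is an event that was transient and untreated, fell between visits, and is known to the partner but not reported by the subject. Nothing in the visit procedure asks for it.

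**Step 4. Scale, on assumptions only.** Let d be the share of subjects who under-report and s the proportion of their events that is captured by all routes, with full capture in everyone else. The documents give neither value. Overall capture = 1 - d(1 - s), and observed incidence = true incidence x overall capture, taking the same true incidence in both groups.

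| d | s = 0.9 | s = 0.7 | s = 0.5 |
|---|---|---|---|
| 0.3 | 0.97 | 0.91 | 0.85 |
| 0.6 | 0.94 | 0.82 | 0.70 |
| 0.9 | 0.91 | 0.73 | 0.55 |

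A preferred term with true incidence 5% would be observed at 5 x 0.97 = 4.85% at one end and 5 x 0.55 = 2.75% at the other. The first is negligible and the second is not. The documents cannot say where the trial lies.

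**The case against.** The strongest reply is that 7.5.1 sets a minimum and excludes nobody. The binding sentence covers all observed and all reported events, whoever reports them. The question to the subject is a recommendation with an example. The partner has agreed to take part in study assessments (criterion 4d), and adverse-event assessment is scheduled at every visit. A competent site would ask the partner, and a site manual not available here may say so. This stands as far as it goes: half of the remedy, recording what either person reports, is already required. It does not supply the other half, which is asking.

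The objection does defeat several stronger readings that a reader might infer.
- *That TEAEs are under-ascertained.* The documents support a risk of unknown size, not a result.
- *That the whole population has dementia.* SAP 5.3.4 provides for subjects without dementia (MMSE of 25 or more), and an MMSE category of 10 or below does not show how many such subjects enrol.
- *That this is the only assessment that leaves the partner out.* The C-SSRS and MMSE also name no partner, and the follow-up call does include one.
- *That declining cognition would make tolerability appear to improve.* SAP 14.1 tabulates TEAEs by cohort and overall, and plans no summary by time of onset. Both cohorts get the same question, so the cohort display is not obviously distorted either.
- *That terms would drop out of the 2% and 5% tables.* This depends on choosing incidences near the cut-offs. With N = 750 the 5% table needs 38 subjects. A term with true incidence 5% reaches it with binomial probability 0.49 at full capture, 0.25 at capture 0.9 and 0.016 at 0.7; a term at 10% still reaches it with probability 0.987 at 0.7. All TEAEs are in any case tabulated by SOC and preferred term without a threshold, and every event is listed.

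**Conclusion.** The point holds as a gap in active elicitation. The scripted visit question omits an informant whom the protocol requires, and whom it uses for the same endpoint in the follow-up call. TEAE incidence in cognitively impaired subjects is at risk of underestimation, mainly for transient, untreated events between visits. The size cannot be settled from the documents: the range of 0.55 to 0.97 for overall capture rests wholly on assumed values of d and s. No sample size, test or error rate is affected. The point rests on the text as it stands, and would fall away if a site instruction outside these documents already directs the question to the partner.

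**What to change.** Reword 7.5.1 so that the open question at each visit is put to both the subject and the study partner/caregiver, in line with Section 6.4, and record on the adverse-event page who reported each event. A site instruction could serve instead of an amendment if the sponsor's procedures allow it.

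No new visit, staff or procedure is needed. Criterion 5 already expects that the subject can attend with a partner, and the partner completes ratings at Baseline and Weeks 12, 28 and 52. There are three costs.
- Slightly more adverse events will be recorded.
- A protocol amendment goes to the IRB/EC and normally awaits approval (Protocol 10.7).
- Ascertainment would change part-way: SAP 16.1 reports 231 rolled-over subjects in the first interim analysis and 353 for the second.

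Record the date on which the change takes effect, by site if it differs, so that the report can distinguish events elicited before and after it. If the change is no longer practicable, the report should state that visit elicitation was directed to the subject.
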